6.6.3 Safety data

With respect to safety evaluations, it is not planned to impute missing values. For safety data that are displayed by time point (or visit) of measurement, the OC-IR approach will be used. For safety data that are not displayed by visit such as AE and possibly clinically significant laboratory abnormality, OR will be used.

The only exceptions where imputation might be necessary for safety evaluation are AE dates and start and stop dates for concomitant medications. Missing or incomplete AE dates are imputed according to BI standards. (4)

Partial start and stop dates for concomitant medications, rescue, and historical medication for HS will be imputed to enable subsequent calculation (but not for display) by the following "worst case" approach:

Proprietary confidential information © 2021 Boehringer Ingelheim International GmbH or one or more of its affiliated companies

- If the day of the end date is missing, then the end date is set to last day of the month (or to the patient's trial completion date, if it is earlier than the last day of the month).
- If the day and month of the end date are missing then the end date is set to 31st of December of the year (or to the patient's trial completion date, if it is earlier than the 31st of December of the year).
- If the day of the start date is missing then the start date is set to first day of the month (except for rescue therapy, where the first dosing day will be used if first dosing happened in the same month).
- If the day and month of the start date are missing then the start date is set to 1st January of the year (except for rescue therapy, where the first dosing day/month will be used if first dosing happened in the same year).
- All other cases need to be assessed by the trial team on an individual basis, using the above points as guidance.

If a concomitant medication was ticked to be ongoing, it is expected that the end date is missing and will not be imputed for display purposes.

6.6.4 PK data

Missing data and outliers of PK data are handled according to BI standards (see 001-MCS-36-472_RD-01) ([5](#)).

6.6.5 Biomarker data

The handling of other biomarkers e.g. RNA expression will be specified in a separate document.

6.6.6 Time since first diagnosis

For incomplete information on the date of first diagnosis, time since first diagnosis will be calculated as follows:

- If the year of first diagnosis is unknown, time since first diagnosis will be set to missing.
- If day and month of the first diagnosis are unknown, time since first diagnosis will be calculated as if diagnosed on the 30th June of that year.
- If only the day of the first diagnosis is unknown, time since first diagnosis will be calculated as if diagnosed on the 15th of that month.

6.7 BASELINE, TIME WINDOWS AND CALCULATED VISITS

Measurements reported with date and time and taken prior to start of administration of trial treatment will be considered pre-treatment values. Measurements reported with a date only (and no time) and taken on the day of first administration of trial treatment will also be considered pre-treatment values. These pre-treatment values will be assigned to visits according to the nominal visit number as recorded on the eCRF or as provided by the laboratory.

Baseline, unless otherwise specified, is defined as the last measurement collected prior to the start of administration of the trial treatment.

Proprietary confidential information © 2021 Boehringer Ingelheim International GmbH or one or more of its affiliated companies
 Measurements taken after start of administration of trial treatment will be considered either on- or off-treatment values based on the definition in [Section 6.1](#), and will be assigned to visits for statistical analysis, if applicable, as defined below.

Analysis of AE data, potentially clinically significant abnormal laboratory values, concomitant medication or non-drug therapies, as well as use of rescue therapy will not be based on visits. Frequency tables for these data will be using on-treatment data and categorized based on their occurring/starting dates. Therefore, no assignment to time windows will be necessary for such data.

The derivation of the last value, minimum value and maximum value of laboratory and vital signs data will consider all on-treatment values (whether or not selected in any time window; see [Table 6.1: 1](#) for definition of the on-treatment period) within the period of interest; these will be derived for analysis of laboratory and vital signs data.

All other safety, efficacy and biomarker measurements will be assigned to visits based on extended time windows around the planned visit dates, defined relative to the day of first trial treatment (which is scheduled for Visit 2). These extended time windows are defined in [Table 6.7: 1](#).

Table 6.7: 1 Time windows for assignment of efficacy, safety lab, vital signs and biomarker to visits for statistical analysis

Visit number	Visit label	Planned day	Time window				
			Window (per CTP)	Start (per CTP)	End (per CTP)	Start (extended)	End (extended)
1	screening	-28 to-1					
2	Week0	Day1	none	1 ^A	1	1 ^A	1
3	Week1	Day 8	+1	7	9	2	11
4	Week2	Day15	[contact]
5	Week4	Day29	[contact]
6	Week6	Day43	[contact]
7	Week8	Day57	[contact]
8	Week10	Day71	[contact]
9 ^C	Week12 (EoT)	Day85	[contact]	Week20 (FUP1)	Day141	[contact]	Week 28 (EOS)	Day197	[contact]
For patients who discontinue the treatment early and are not willing to follow the whole visit schedule:							
-	EOS	LD ^B +112	-	-	-		

All days are counted relative to the day of randomized treatment, which is defined as Day 1.

^A Note that measurements made at Day 1 and assigned to the on-treatment period (because mistakenly made after start of trial treatment) via assessment on date & time (i.e. safety laboratory) will not be assigned to Day 1. Such data will be listed only.

^BLD= Last dose.

^C For the patients who enter extension trial, the EOT will be the last visit (i.e., V10 and V11 are not required). The EOS (=individual end of the study) will be the first administration of the trial drug in extension trial.

Proprietary confidential information © 2021 Boehringer Ingelheim International GmbH or one or more of its affiliated companies

Repeated and unscheduled efficacy, safety and biomarker measurements will be handled similarly to scheduled measurements and will also be assigned to a time window depending upon the date of measurement.

Only one observation per time window will be selected for statistical analysis at a particular visit – the value which is closest to the protocol planned visit day will be selected. If there are two observations which have the same difference in days to the planned day, the later value will be selected. If there are two observations on the same day, the worst value will be selected.

Assignment of observations to visits based on time windows will be based on the non-imputed (observed) data after the implement of estimand concept. For example, for EC and OC methods, values after rescue therapy intake should be censored first before assignment of efficacy endpoints.

For visits without an assigned value based on time windows, a value will thereafter be imputed as defined in [Section 6.6](#). Imputation of efficacy endpoints, when applicable, will be performed based on all available observations meeting the imputation rules, irrespective of whether the observation was selected in any time window.

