3 X^c is a complete physical examination. X^t is a targeted physical examination. See [section 5.2.1](#).

4 Measurements of vital signs should precede blood sampling to avoid the impact of blood sampling on the vital measurements at all dosing visits. Additional assessments of vital signs should be performed at 10 minutes post-dose for s.c administrations and 5 minutes and 1 hour post dose for i.v. administrations.

5 Women of childbearing potential only. A serum pregnancy test will be performed at screening. Urine pregnancy tests will be performed at all other visits indicated in the [Flowchart](#). In case of a positive urine pregnancy test, a serum pregnancy test will be done. Urine pregnancy testing should be done prior to administration of study drug. Study drug should only be administered in case of a negative test result. More frequent testing should be done if required by the local regulation or per investigator judgment.

6 It is preferred but patients do not have to be fasted for the blood sampling for the safety laboratory. At visits with study drug administration this should be done prior to the study drug administration. See [Table 5.2.3:2](#) for detailed information of the tests. If needed, safety lab samples for Visit 2 can be drawn within 48 hours before the actual visit date.

7 Infection Testing: At screening and at EoT visit. See section safety laboratory parameters for complete list of testing required (see [Table 5.2.3:1](#)).

8 Patients who terminate study drug early should do the EoT visit as soon as possible. These patients will then do FUP1 and EoS visits, 8 and 16 weeks after last study drug administration respectively.

9 At study visits with study drug administration, pre-dose PK/ADA/Nab samples will be obtained approximately within 1 hour prior to start of i.v. infusion or s.c. injection.

10 Desoxyribonucleid Acid (DNA) banking sample is optional. This sampling is only possible if the patient agreed by signing a separate informed consent. For details please see [Section 5.5](#).

11 At selected sites, where ultrasound is available, it is required to do ultrasound lesion evaluation and to guide biopsies. At sites without ultrasound capabilities, biopsies will be done without ultrasound guidance.

12 At Screening, the C-SSRS baseline/screening scale will be completed. At all subsequent visits the “Since last visit” scale will be completed.

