4.1.4 Drug assignment and administration of doses for each patient

Patients will be treated with spesolimab or matching placebo as indicated in the [Flowchart](#) and [section 3.1](#).

The medication will be assigned via IRT.

Patients will receive i.v. spesolimab at week 0, 1 and 2.

Detailed instructions for the preparation of the solution for infusion, the volume to be administered and the infusion rate are provided in the ISF.

Patients will receive spesolimab s.c. injections at week 4, 6, 8 and 10.

Injection site should not be close to a vein and it should avoid sites where the skin is tender, bruised, erythematous, or indurated, and should be alternated to other areas for subsequent doses.

Detailed instructions for use and handling of spesolimab syringes are provided in the ISF.

Patients have to be closely monitored for local or systemic hypersensitivity reactions for 1 hour following s.c. or i.v. study drug administration. Patients should be closely monitored for signs and symptoms of injection site or systemic hypersensitivity reactions following study drug administration. Study personnel should observe the injection site for signs of redness, swelling or hardness. They should also ask subjects about itching, dizziness or shortness of breath. Patients should be advised that if they experience redness, swelling or other changes

at the injection site, they should notify site personnel. They should further be advised that if they experience itching all over or a feeling of being swollen, dizzy or short of breath, they should seek emergency medical attention immediately and notify site personnel.

The administration of the trial medication on all applicable study days will be done under supervision of the investigating physician or a designee at the site. If available, a pharmacist should prepare the study medication. The so-called four eye principle (two-person rule) should be applied for preparation (e.g. choosing the correct vials with the correct medication number) and administration of trial medication.

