5.2.2 Vital signs

Vital signs will be evaluated at the time points specified in the [Flowchart](#), prior to blood sampling.

This includes temperature, respiratory rate, systolic and diastolic blood pressure and pulse rate (electronically or by palpation count for 1 minute). Respiratory rate, pulse rate, and blood pressure will be measured after patients have been sitting comfortably for at least five minutes. The results must be included in the source documents available at the site. Measurement of vital signs should precede blood sampling to avoid the impact of blood sampling on the vital measurements.

Vital signs will be measured additionally 10 min post-dose after s.c. administration and 5 and 60 min. post-dose in case of i.v. study drug administration.

Hypersensitivity reactions should be treated according to medical standards. Pre-medications for further injections might be considered and will be agreed on between investigator and the Sponsor.

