7.8 SAFETY ANALYSIS

All safety analyses will be performed on the safety analysis set.

All safety analyses will be performed following BI standards. No hypothesis testing is planned. OC-IR and OR methods will be used for safety reporting. All safety analysis will be performed for on-treatment period.

AE and possibly clinically significant laboratory abnormalities will be analyzed under OR (as defined in [Section 6.6.3](#)); the safety data by visit, i.e., laboratory, vital signs and local tolerability, will be analysed under OC-IR (as defined in [Section 6.6.3](#)).

As the onset time of an AE will not be collected in the trial, any AE which occurs on the same day as a treatment dose will be assigned to the “post treatment”. For safety assessments by visits, if time is not collected, data on the same day of a treatment dose will be treated to be “prior treatment” except for scheduled local tolerability and post-dose vital signs assessments.

Off-treatment data will be listed only.

Additional analyses on AE will be also included:

AE within loading stage

Proprietary confidential information © 2021 Boehringer Ingelheim International GmbH or one or more of its affiliated companies
For AE, the additional safety tables for loading dose stage will be produced by grouping patients based on their loading doses (1200 mg, Placebo) using SAF. The outputs will include on-treatment data up to the first maintenance dose at or post week 4. If patients discontinued from treatment prior to receiving first maintenance dose, then the safety data up to the date of last loading dose + 112 days will be included.

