7.8.3 Vital signs

The analyses of vital signs (blood pressure, pulse rate, body temperature, respiratory rate) and body weight will be descriptive in nature. Descriptive statistics of vital signs over time and for the difference from baseline (see [Section 6.7](#)) will be provided, including the last value, the minimum value and the maximum value during on-treatment period.

Clinically relevant findings in vital signs data will be reported as baseline conditions (at screening) or as AEs (during the trial) if judged clinically relevant by the investigator, and will be analysed as such.

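### The same-day worst-value rule in SAP 6.7 pools scheduled pre-dose and post-dose vital signs in the by-visit tables, and no pre-to-post-dose change is planned

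*SAP*

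**What the plan says.** **Schedule.** The protocol Flowchart (footnote 4) places a vital-signs reading before blood sampling at each dosing visit and then requires further readings: "vital signs should be performed at 10 minutes post-dose for s.c administrations and 5 minutes and 1 hour post dose for i.v. administrations". Protocol 5.2.2 repeats this. Infusions are given at Weeks 0, 1 and 2, and subcutaneous doses at Weeks 4, 6, 8 and 10 (protocol 4.1.4).

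**Selection rule.** Table 6.7:1 in SAP 6.7 names vital signs in its title. One observation is chosen per window: the one nearest the planned day, or the later one if two are equally near. For the same day the text reads: "If there are two observations on the same day, the worst value will be selected". Scheduled pre-dose and post-dose readings are not distinguished.

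**Day 1.** Footnote A of that table says that Day 1 measurements falling in the on-treatment period because they were taken late by mistake (safety laboratory is the instance given) "will not be assigned to Day 1. Such data will be listed only". The extended Week 1 window opens on Day 2.

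**Other summaries.** SAP 6.7 derives the last, minimum and maximum vital signs from all on-treatment values, whether or not a window selected them. SAP 7.8 counts untimed same-day data as pre-dose, "except for scheduled local tolerability and post-dose vital signs assessments". SAP 7.8.3 plans "Descriptive statistics of vital signs over time and for the difference from baseline", together with the on-treatment last, minimum and maximum. It names no post-dose timepoint.

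**The concern.** A by-visit table should compare like with like. Here the number of readings behind each tabulated value depends on the dosing schedule: one at baseline, three at Weeks 1 and 2, two at Weeks 4 to 10, and one again at Week 12. Taking the worst of several readings moves a mean even when nothing has happened to the patient.

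The rule also blurs the information that the post-dose readings were scheduled to give. Systemic hypersensitivity including infusion reaction is an adverse event of special interest, and protocol Appendix 10.13 counts reduced blood pressure among the anaphylaxis criteria. If 'worst' is taken as highest, a fall after an infusion loses to the higher pre-dose reading. If it is taken as lowest, a rise is lost. The SAP does not say which applies. The sentence also speaks of two observations, whereas an infusion visit has three. No planned summary shows the change from before to after a dose.

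**Working it through.** The documents give no figure on this point, so there is none to reproduce. The check counts readings from the schedule, applies the SAP rules to them, and then illustrates the size.

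**1. Scheduled readings per patient on dosing days**

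- Infusion visits: 3 visits × (1 pre-dose + 2 post-dose) = 9.
- Subcutaneous visits: 4 visits × (1 pre-dose + 1 post-dose) = 8.
- Total: 9 + 8 = 17, of which post-dose 3 × 2 + 4 × 1 = 10.
- Of these 10, 2 fall on Day 1, 2 × 2 = 4 at Weeks 1 and 2, and 4 × 1 = 4 at Weeks 4 to 10.

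**2. What reaches the by-visit tables**

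| Visit | Scheduled same-day readings | Value tabulated under SAP 6.7 |
|---|---|---|
| Baseline | 1 before first dose | that reading |
| Weeks 1, 2 | 3 | worst of 3 |
| Weeks 4, 6, 8, 10 | 2 | worst of 2 |
| Week 12 | 1 | that reading |

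Eight post-dose readings therefore compete with a same-day pre-dose reading. The two Day 1 post-dose readings are on-treatment, because that period begins with the first loading dose (SAP Table 6.1:1). If footnote A applies to them, they are barred from Day 1, and the Week 1 window has not yet opened. If it does not apply, they sit in the Day 1 window beside the pre-dose reading, under the same worst-value rule. Neither result gives a usable by-visit display.

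**3. Illustrative shift with no true change**

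Take same-day readings as normal with equal means, total SD σ and within-day correlation ρ (assumed, 0 to 0.9), and take 'worst' as highest. The expected shift is c × σ × √(1 − ρ), where c is the expected maximum of k standard normals: 0.564 for k = 2 and 0.846 for k = 3.

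| ρ | worst of 2 | worst of 3 |
|---|---|---|
| 0 | 0.56 SD | 0.85 SD |
| 0.5 | 0.564 × 0.707 = 0.40 SD | 0.846 × 0.707 = 0.60 SD |
| 0.9 | 0.564 × 0.316 = 0.18 SD | 0.846 × 0.316 = 0.27 SD |

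A simulation of 400,000 draws gave the same values to two decimals, apart from rounding at ρ = 0 (0.565 and 0.845). The value kept was a post-dose one in 50% of subcutaneous visits and 67% of infusion visits.

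In mmHg, assume a within-visit SD of 6 for systolic pressure (range 4 to 8; not from the documents) and independent within-visit deviations:

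- Weeks 1 and 2: 0.846 × 6 = 5.1 mmHg (3.4 to 6.8).
- Weeks 4 to 10: 0.564 × 6 = 3.4 mmHg (2.3 to 4.5).
- Week 12: 0.

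If 'worst' means lowest, the sign reverses.

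**The case against.** Several points on the other side stand.

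- A reader might infer that Day 1 post-dose readings are only listed, or that the first infusion is missing from the vital-signs summaries. The documents do not support that. Footnote A is worded for measurements taken late by mistake, and scheduled 5- and 60-minute readings are not mistakes. SAP 6.7 brings every on-treatment value into the last, minimum and maximum, and SAP 7.8.3 reports these.
- A reader might infer that infusion reactions would go unseen. They are an AESI with separate tables. SAP 7.8.1 adds hypersensitivity and anaphylaxis searches, SAP 7.8 adds adverse-event tables for the loading stage, and SAP 7.8.3 has clinically relevant vital-sign findings analysed as adverse events. An external DMC reviews unblinded safety data.
- A reader might infer a biased comparison of the arms. With no drug effect the shift is the same in both arms.
- SAP 7.8 treats scheduled post-dose vital signs as a class of their own, so the authors had them in mind. Company reporting standards that are not reproduced in the SAP may also govern the final display.

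These points narrow the concern but do not remove it. SAP 7.8 classifies the post-dose readings without giving them a place in any table. The last, minimum and maximum span an on-treatment period that can run to 112 days after the last dose, so they show neither which dose a value followed nor the change from before it. The adverse-event route depends on the investigator judging a finding clinically relevant. A standard that is not stated cannot be assumed to override a selection rule that is.

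**Conclusion.** The concern holds as a defect in the by-visit display of vital signs. Followed as written, SAP 6.7 mixes pre-dose and post-dose readings at six visits (Weeks 1, 2, 4, 6, 8 and 10) and compares the result with a single baseline reading. The trend over visits and the change from baseline are distorted, 'worst' is undefined for two-sided parameters, the Day 1 post-dose readings lack a clear by-visit slot, and no pre-to-post-dose change is planned.

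The counts follow directly from the schedule. The size of the shift does not: it rests on an assumed correlation or within-visit SD and on a chosen direction for 'worst', so the mmHg figures are illustrative only.

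The analysis is descriptive, and no efficacy endpoint depends on it. The point should be corrected before the tables are programmed, but it does not threaten the trial's main conclusion.

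**What to change.** In SAP 6.7, exempt scheduled post-dose vital signs from the same-day worst-value rule and from footnote A, and state that the by-visit trend and change from baseline use the pre-dose reading at dosing visits.

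In SAP 7.8.3, add one descriptive table by arm of the change from the same-visit pre-dose value to each scheduled post-dose timepoint: 5 and 60 minutes after infusion, including Day 1, and 10 minutes after subcutaneous dosing. Keep the on-treatment last, minimum and maximum as planned.

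The cost is SAP wording and one extra table from readings that the protocol already schedules. Trial conduct does not change.

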7. PLANNED ANALYSIS

The following analyses of this trial protocol are planned:

Primary Analysis

The primary analysis will be performed once all patients have either 1) completed the 12 weeks treatment period or 2) have reached the 12 weeks after starting of treatment if early discontinued the trial treatment; for this assessment a first database lock (before the final database lock) will be performed.

The primary analysis will be performed by the sponsor. The project and trial team members will be un-blinded for treatment information and this analysis.

Note that biomarker data may be reported in a separate biomarker report at this time. If applicable, details of these analyses will be provided in a separate Biomarker Statistical Analysis Plan.

Final analysis

Final trial analysis will be performed once all randomized patients have completed the trial; at that time point, a final database lock will be done.

If separate primary analysis and final analysis, comprehensive analysis will be performed in the primary analysis. All data up to the cut-off date will be included for analysis. In final analysis, only concomitant medication/therapy and safety listings will be provided for these ongoing patients before trial completion at the time of database lock for primary analysis. A final clinical trial report will be written for all data from primary analysis and final analysis.

The primary analysis and final analysis may be performed as a single analysis (at the time of trial completion), if insufficient time interval between the two planned analysis and agreement by the trial team not to perform two separate analyses before the time of the primary analysis. For example, majority of patients enter the extension study and no patient is ongoing under REP at time of DBL of primary analysis.

The decision will be described and documented in final CTR.

General Remarks

The format of the listings and tables will follow the BI guideline "Standards for Reporting of Clinical Trials and Project Summaries " (*BI-KMED-BDS-HTG-0045*) ([10](#)) and those generated for PK are based on 001-MCS-36-472 ([5](#)).

The individual values of all patients will be listed. Listings will generally be sorted by country, center number, patient number and visit (if visit is applicable in the respective listing). AE listings will be sorted by assigned treatment (see [Section 7.8.1](#) below for details). The listings will be contained in Appendix 16.2 (SDL) of the CTR.

The following standard descriptive statistical parameters will be displayed in summary tables of continuous variables:

Proprietary confidential information © 2021 Boehringer Ingelheim International GmbH or one or more of its affiliated companies

N	number of non-missing observations
Mean	arithmetic mean
SD	standard deviation
Min	minimum
Q1	lower quartile
Median	median
Q3	upper quartile
Max	maximum

For PK analyte concentrations, the following descriptive statistics will additionally be calculated: variables:

CV:	arithmetic coefficient of variation
gMean:	geometric mean
gCV:	geometric coefficient of variation

The data format for descriptive statistics of concentrations will be identical with the data format of the respective concentrations.

Statistical parameters will be displayed to a defined number of decimal places as specified in the BI guideline "Standards for Reporting of Clinical Trials and Project Summaries." ([10](#))

Tabulations of frequencies for categorical data will include all possible categories and will display the number of observations in a category as well as the percentage (%) relative to the respective treatment. Percentages will be rounded to one decimal place. The category missing will be displayed if and only if there actually are missing values. Percentages will be based on all patients in the respective patient set whether they have non-missing values or not.

Disposition of the patient population participating in the trial will be summarized by the presentation of the frequency of patients screened, randomized, screened but not randomized, randomized but not treated, randomized and treated, who completed randomized medication, who withdrew from the trial before EOT visit, by reason, who were prematurely discontinued from trial medication, by reason, who received rescue therapy for HS worsening and who entered the extension trial 1368.67.

The frequency of patients with iPDs, also summarized by whether or not the iPD led to exclusion from the PPS, will be presented.

The frequency of patients in each of the different analysis sets will also be presented.

